## Analysis of secondary outcomes

Continuous measures over time will be modeled with HLM methods described above. Health service use can be categorized into binary (e.g., met threshold for medication possession ratio, had > 1 hospitalization) and count outcomes (e.g., N of ED visits, primary care visits). Binary outcomes will be modeled with multivariable logistic regression, and the coefficient of study arm membership (e.g, 0=TAU, 1= TAU+BLT+AP & TAU+BLT) is the coefficient of primary interest. Count outcomes are modeled with either multivariable Poisson or negative binomial regression depending on which yields optional fit.

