If motivation to adhere to the BLT protocol is lacking, coaches will employ brief MI. Many of our behavioral health and assessment (BAC) staff have delivered MI and adherence promotion protocols similar to this for previous trials. While BAC staff have prior MI experience, they will also attend MI workshops offered by KPNW and will then be trained by senior staff to address MI specifically for BLT use. We have engaged a MI fidelity expert, [name] to rate training cases and ongoing calls to confirm initial and ongoing coach MI fidelity. During start-up each coach will conduct several simulated BLT coaching calls; [name] will rate audio recordings of these simulations for MI quality/adherence. Staff who are rated 4 or higher on four global components of MI quality/adherence for these initial simulations will be cleared to conduct study MI with enrolled participants. We will also conduct ongoing MI fidelity ratings for study Arm 3 phone coach contacts. [name] will conduct MI fidelity reviews of a random 10% selection of these Arm 3 coaching calls (blocked by coach, and by early/late session). Additionally, as [name] reviews MI sessions she will also complete fidelity checklists (to be created and submitted in a subsequent modification) of BLT health education review/practice and problem solving that coaches may deliver to promote ideal BLT sessions (e.g., did coach review whether daily BLT sessions occurred? If not, were barriers identified and possible solutions explored?). [name] MI fidelity and BLT education ratings will be used as process variables, but also to provide feedback to coaches during supervision meetings.

Based on prior coaching experiences, ~10% of individuals randomized to Arm 3 will likely not engage with coaches, despite indicating a previous willingness to do so. Coaches attempt to reach all Arm 3 participants, but after 3 failed outreach attempts coaches will send a final "contact us if you wish" email or letter.

Assessments

We will ask participants to complete baseline and follow-up surveys using the REDCap online survey system; those who do not complete the online surveys after 3 prompts will be called by interviewers and verbally administered the same scales. Assessments consist of the baseline assessment; a post-acute treatment assessment at 2 months after enrollment; and follow-up assessments at month 4 and month 6, for a total of 4 data points over the course of six months. Interviewers will be blinded to study condition.

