Demographics data will be collected on all potential participants during the screening process and/or baseline assessment and will include race, ethnicity, sex assigned at birth, gender identity, relationship status, employment status, and education and income information.

Survey Measures

All measures will be administered at the baseline assessment and all follow-up assessments unless otherwise indicated. The surveys will include questions from the following measures, either in part or in their entirety: **Patient Health Questionnaire-9 (PHQ-9); Seasonal Pattern Assessment Questionnaire (SPAQ); Quick Inventory of Depressive Symptomatology, self-report (QIDS-SR); Geriatric Depression Scale (GDS);** the abbreviated **self-report Columbia Suicide Severity Rating Scale (C-SSRS); Altman Self-Rating Mania Scale (ASRM); Generalized Anxiety Disorder-7 (GAD-7); Brief Medication Questionnaire (BMQ); Short Form 6 Dimension (SF-6D); Pittsburgh Sleep Quality Index (PSQI); Reduced Version of the Morningness-Eveningness Questionnaire (rMEQ); Split Week Self-Assessment of Sleep Survey (SASS-Y); Readiness Ruler (RR);**

Non-Standardized Measures to be collected include:

Alternative depression treatments. We will ask participants whether they are currently using, or intend to use, any “alternative” treatments for depression such as BLT (including whether light box purchase was new or had existing), yoga, Tai Chi, mood-enhancing diets (e.g., Mediterranean Diet), exercise, omega-3 fatty acids, St John’s wort, and others.

Satisfaction and Feedback. At the 2-month follow-up assessment, we will ask participants in Arms 2 and 3 about their experience as a participant in this study.

Actigraphy

Following the baseline and 2-month follow-up assessments, participants will be mailed an actigraphy device to wear for 10 days or until the battery dies and then return in supplied postage-paid envelope. We will download/score actigraphy data for sleep and physical activity using ActiLife software, then reset the actigraphy device and reuse it again with additional participants.

Ecological Momentary Assessment (EMA)

Up to 4 days per week during the 9-week acute intervention phase (baseline to 2-month follow-up), and twice weekly thereafter to 6 months, all participants will be sent text and/or email links to a brief EMA REDCap survey about mood and sleep in the last 24 hours. For participants in Arms 2 and 3, the EMA survey will also include brief questions about BLT adherence.

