# INTRODUCTION

This statistical analysis plan provides guidelines for the final presentation and analysis for the BLT Pilot Trial. The R34 pilot was designed to prepare for a future, fully-powered effectiveness trial. This study collects information to conduct the BLT Pilot Trial as described in these following aims:

Aim 1.1: We will enroll 90 depressed patients in this modest-size feasibility pilot, and randomize them to:

- Arm 1: Treatment as Usual (TAU) control: A “usual care” control group (e.g., antidepressants, watchful waiting, psychosocial therapy; all TAU will be recorded for all participants in all study conditions); or
- Arm 2: TAU + Minimal BLT Encouragement: TAU plus two minimal communications (mailed letter, secure EHR message) identifying BLT as a promising treatment, and outlining steps for patients to self-initiate. Arm 2 will not include any phone coaching or adherence promotion.
- Arm 3: TAU + Enhanced BLT Encouragement + Adherence Promotion + MI: TAU plus 2-4 brief calls to encourage BLT use, advise on purchase of a light box (LB), assist with obtaining insurance reimbursement, educate for correct LB use, and provide motivational interviewing (MI) as needed to promote adherence.

Aim 2. This small pilot sample is insufficient for confirmatory tests. However, we will conduct analyses that mirror those planned for a future, fully-powered trial. Key analytic contrasts are (a) active Arms 2 + 3 vs. control Arm 1; (b) each active Arm (2, 3) separately vs. control Arm 1; and (c) Minimal Arm 2 vs. Enhanced Arm 3. For each contrast we will initially examine differences between study arms in pre-post change in proposed mediators in BLT and MI effects; followed by examination of differences in pre-post change in the primary (PHQ-9) and key secondary outcomes (see Assessment). We then examine candidate mediators (improved sleep, normalized circadian rhythm, increased physical activity, readiness for change) for mediating BLT and MI effects on depression. We will also examine moderation of BLT effects and subgroup outcome variation (e.g., receiving vs. not receiving TAU ADs). Pilot feasibility data will facilitate rapid launch of a future trial: estimated recruitment, retention, and adherence with BLT protocol; and a cautious estimate (with wide confidence intervals) of BLT effectiveness.

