## Analysis of primary outcome

For our PHQ-9 primary outcome, we will test whether there are differences in score trajectories across time between arms with two-level hierarchical linear models (HLMs) in a growth curve framework[7-9]. The first level of the model will include time as a predictor, modeling within-person variation. The second level will include a dummy variable for arm (e.g., 1=TAU+BLT+AP or TAU+BLT, 0=TAU) as the predictor variable for both the random effects of the intercept and slope for time. A significant coefficient for arm on the time slope would indicate that there are different trajectories across time for BLT arms versus TAU. We will probe any significant arm x time interactions by graphing the simple-effects equations to determine whether the observed pattern is consistent with hypotheses. Compared to the Arm 1 TAU condition, a pattern in which the active arms (Arms 2 and 3) exhibit a greater PHQ-9 decrease over time supports the effectiveness of the intervention. However, recall this pilot is insufficiently powered to formally test intervention effects[1-3].

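### Actigraphy has only two waves: as wave summaries, the SAP's growth model has one variance parameter too many and reduces to a change-score comparison

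*SAP*

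**What the plan says.** - **Schedule.** Protocol section 6, Actigraphy: "Following the baseline and 2-month follow-up assessments, participants will be mailed an actigraphy device to wear for 10 days or until the battery dies". That is two waves. The surveys have four occasions: "All measures will be administered at the baseline assessment and all follow-up assessments unless otherwise indicated" (Survey Measures), "for a total of 4 data points over the course of six months" (Assessments).
- **What actigraphy supplies.** "We will download/score actigraphy data for sleep and physical activity using ActiLife software". No other listed instrument measures total physical activity.
- **Arm contrasts on mediators.** Under Aim 2 in the SAP's Introduction, each contrast will "initially examine differences between study arms in pre-post change in proposed mediators". Protocol section 2 has the same step. Neither names a model.
- **General rule for continuous measures.** SAP, Analysis of secondary outcomes: "Continuous measures over time will be modeled with HLM methods described above". The Protocol's Data Analysis section repeats it. Neither makes an exception for measures with fewer than four occasions.
- **The model referred to.** SAP, Analysis of primary outcome: a two-level HLM in which time is the level-1 predictor and arm enters "as the predictor variable for both the random effects of the intercept and slope for time".
- **A different model for mediation.** SAP, Moderation and mediation, lists actigraphic sleep and physical activity among the mediators. Its worked example regresses the post-treatment mediator (ISI in the SAP, PSQI in the Protocol) on its baseline value and arm.

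**The concern.** A random-intercept, random-slope model needs more than two occasions per person to separate slope variance from residual variance. The only arm-contrast rule that the plan gives for continuous measures carries that model forward without asking how many occasions a measure has. Applied to two-wave actigraphy summaries, it asks the software for variance components that the data cannot supply.

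Three things are at stake. The analyst would meet the problem in each of the 10 imputed datasets and would have to choose a replacement after seeing data. The same actigraphy variable could be analysed one way in the arm contrast and another way in the mediation step. And the effect that can be recovered from the growth model does not use the first-wave value as efficiently as it could. The SAP runs these analyses partly to show that they are feasible for the full trial, so a model that does not fit the measurement schedule is worth correcting now.

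**Working it through.** The documents give no figure for actigraphy, so there is nothing to reproduce. The check is of identifiability, followed by precision.

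**Inputs.** Two actigraphy waves (Protocol section 6, Actigraphy). Random intercept, random slope and residual (SAP, Analysis of primary outcome). Allocation 1:1:1 (Protocol section 6, Randomization). Retained N = 81, two-sided alpha 0.05, power 80% and correlation 0.70, the last stated for the PHQ-9 only (SAP, Power analysis). Assumed: one summary value per wave, and equal variances at the two waves.

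**1. Count of parameters.** Let the waves be at times 0 and t, with intercept variance a, intercept-slope covariance b, slope variance c and residual variance s. Then:

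- Var(y0) = a + s
- Var(y1) = a + 2tb + t²c + s
- Cov(y0, y1) = a + tb

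There are three equations in four unknowns. The Jacobian has rank 3 for 4 parameters at times 0, 2. It has rank 4 at times 0, 2, 4 and at 0, 2, 4, 6.

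**2. The direction that the data cannot see.** Add δ to s, subtract δ from a, add δ/t to b and subtract 2δ/t² from c. Then:

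- Var(y0) changes by −δ + δ = 0
- Var(y1) changes by −δ + 2δ − 2δ + δ = 0
- Cov changes by −δ + δ = 0

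In one simulated data set (27 vs 54 participants, t = 2), four residual variances gave the same log-likelihood, each with a valid random-effects covariance matrix:

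| s | a | b | c | log-likelihood |
|---|---|---|---|---|
| 0.01 | 0.8106 | −0.0768 | 0.0967 | −182.066356 |
| 0.05 | 0.7706 | −0.0568 | 0.0767 | −182.066356 |
| 0.10 | 0.7206 | −0.0318 | 0.0517 | −182.066356 |
| 0.20 | 0.6206 | 0.0182 | 0.0017 | −182.066356 |

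**3. What happens to the arm effect.** The fixed effects (constant, time, arm, arm × time) have rank 4 of 4 at two waves. In the same data the arm-by-time slope was −0.2014 (SE 0.0761) under random intercept plus slope, under random intercept only, and under the change score divided by t. Because arm also predicts the intercept, the first-wave means are left free in each arm, and arm × time is then the difference in mean change.

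**4. Precision of a change score against baseline adjustment.** Per unit outcome variance, a change score has variance 2(1 − r). The value adjusted for the first wave has 1 − r² = (1 − r)(1 + r). The ratio is (1 + r)/2:

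| r (assumed) | ratio | reduction in variance |
|---|---|---|
| 0.3 | 0.65 | 35% |
| 0.5 | 0.75 | 25% |
| 0.7 | 0.85 | 15% |

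**5. Illustration as a detectable effect.** Borrow r = 0.70 and 81/3 = 27 per arm. The minimum detectable d is 2.8016 × √(1/n1 + 1/n2) × m, with m = √0.6 for change and √0.51 for adjustment.

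- Arms 2+3 vs 1 (54 vs 27): 0.6603 × √0.6 = 0.51 for change; 0.6603 × √0.51 = 0.47 for adjustment.
- Single arms (27 vs 27): 0.7625 × √0.6 = 0.59 for change; 0.7625 × √0.51 = 0.545 for adjustment.

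**The case against.** The strongest reply is that the plan already has a two-wave method for these variables. The mediation section names actigraphy and activity, and its example is a baseline-adjusted regression whose arm coefficient is the quantity wanted. The rule quoted above sits under secondary outcomes, no section calls actigraphy a secondary outcome, and Aim 2 keeps mediators and outcomes apart. This stands in part. The mediation regression is sound with two waves and needs no repair. But it is offered as an example inside the product-of-coefficients analysis and is not assigned to the separate Aim 2 arm contrasts. For those, the general rule is the only arm-contrast model for continuous measures that the plan states.

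A reader might go further and infer that the planned model cannot be fitted, or that the actigraphy contrast is lost. The documents do not support that. Only the split among variance components is undetermined; the arm-by-time effect and its SE survive, as step 3 shows. Nor are the sleep mediators affected as a group: the PSQI, SASS-Y and rMEQ fall under the four-occasion schedule, where the model is identified.

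The unit of data also matters. The Protocol specifies up to 10 days of wear per wave and does not say whether daily records or wave summaries are modelled. With ten daily records per wave the Jacobian has rank 4 and the model is identified. Measurement times that vary between individuals could also identify it, though weakly.

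Finally, mediation is exploratory, and the Protocol says that the pilot is not powered for it. That limits the consequence but does not remove the gap.

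**Conclusion.** The point holds in limited form. If actigraphy is analysed as one summary per wave under the growth HLM for the Aim 2 contrasts on pre-post change, the model is over-parameterised by one variance parameter. It then yields no more than a change-score comparison. Adjusting for the first-wave value instead would cut the variance of the arm contrast by 15% at r = 0.7 and by 35% at r = 0.3. In the illustration, the detectable d falls from 0.51 to 0.47 for the pooled contrast and from 0.59 to about 0.55 for single arms.

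The identifiability result is exact given wave summaries at common times. The precision figures rest on equal variances and an assumed r, and the detectable effects also borrow the PHQ-9 correlation and the 6-month retained sample.

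One caveat applies to either analysis. Both treat the first wave as pre-randomisation, but the device is mailed after the baseline assessment, randomisation also follows that assessment, and Arm 3 coaching ideally begins within 72 hours of enrolment. The documents do not say whether first-wave wear ends before assignment. If it does not, subtracting or adjusting for the first-wave value could remove part of an early effect.

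**What to change.** In the SAP's Analysis of secondary outcomes, and in the matching paragraph of the Protocol's Data Analysis section, add wording to this effect:

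> Actigraphy variables are summarised as one value per wave. Arms are compared by regressing the 2-month value on the first-wave value, arm, and the randomisation strata (gender, age group, minority status). The adjusted difference and its 95% CI are reported for each planned contrast. The growth HLM is used only for measures with four occasions.

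This extends the regression already in the mediation section, so both analyses of actigraphy would use the same form. If the team prefers daily records, the SAP should say so and give the model for them.

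Also state when first-wave wear takes place relative to randomisation and, if some of it falls after assignment, how those days are handled.

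The cost is a few sentences. The analysis becomes simpler, and no data need to be added.

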## BLT process outcomes

To confirm that the Arm 3 adherence/MI elements had their intended effect we will contrast Arms 2 vs. 3 across months 2, 4, and 6, comparing: (a) % cumulative light box purchase; (b) % cumulative DME reimbursement; and (c) mean EMA-adherence (aka, dose). We will conduct these analyses using methods similar to those for secondary outcomes; however, the analysis sample will be restricted to Arms 2 and 3. We will describe similar metrics in the TAU condition (Arm 1) but expect little BLT uptake there.

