Arm 2: TAU + Minimal BLT promotion. Participants will receive 2 brief communications (mailed letter, secure EHR message, email, and/or text) identifying BLT as a promising treatment with few side effects, and steps for participants to self-initiate. The educational and background information from the 2 communications will also be made available as PDFs or webpages on the secure study website. If requested, participants will be provided with a copy of these materials by email. Arm 2 has no phone coaching, adherence promotion or MI.

Arm 3: TAU + BLT encouragement + adherence promotion. BLT promotion coaches will follow a four-

step approach in engaging with Arm 3 participants: (a) provide encouragement to consider using BLT; (b) provide guidance regarding light box purchase and compensation; (c) educate participants about ideal BLT use to obtain maximum benefit; and (d) provide ongoing brief telephonic adherence promotion and motivational interviewing (MI) where warranted to maximize persistent and appropriate BLT use. The educational and instructional information for these 4 steps will also be made available as PDFs or webpages on the secure study website. If requested, participants will be provided with a copy of these materials by email.

Encouragement. Coaches will encourage participants to consider BLT during the first post-randomization contact, in most cases by telephone. Coaches will address the reason for the call (BLT promotion) and advantages of BLT. They will also gauge interest in using BLT; for ambivalent participants they will offer a brief motivational interviewing (MI) exercise.

Compensation for BLT purchase. In Arms 2 + 3 interested participants will receive written guidance on purchasing a light box (LB) that meets minimum study requirements. Arm 3 coaches guide participants to purchase LBs and obtain compensation (up to \$80 in Fred Meyer gift cards) for this cost through the study. This compensation process is modeled to simulate the KP durable medical equipment (DME) benefit, which does not currently cover LBs. Arm 2 offers the same written information about LB purchase and compensation, but no coach assistance.

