We will conduct exploratory analyses of the BLT mediation pathway as the extent to which the relation between BLT and outcomes is mediated by changes in participants' 1) sleep (SASS-Y and actigraphy, and PSQI subjective sleep quality), 2) total physical activity, and 3) circadian timing and chronotype. For example, to evaluate the mediating effect of PSQI sleep quality we will regress post-acute treatment PSQI on baseline PSQI and a randomization condition indicator; and we will regress follow-up PHQ-9 at post-acute treatment PSQI and a randomization condition indicator. Using the product coefficients mediation approach, we will use the resulting regression coefficients and standard errors (SEs) to estimate the indirect effect. Because SEs of the products of regression coefficients are not normal, we will use bias-corrected bootstrapping to estimate the SEs for the indirect effect. We will use a similar approach for the MI pathway to test the mediating effect of participants' increased readiness to change on BLT adherence.

Analysis of secondary outcomes. Continuous measures over time will be modeled with HLM methods described above. Health service use can be categorized into binary (e.g., met threshold for medication possession ratio, had > 1 hospitalization) and count outcomes (e.g., N of ED visits, primary care visits). Binary outcomes will be modeled with multivariable logistic regression, and the coefficient of study arm membership (e.g, 0=TAU, 1=TAU+BLT+AP & TAU+BLT) is the coefficient of primary interest. Count outcomes are modeled with either multivariable Poisson or negative binomial regression depending on which yields optional fit.

BLT process outcomes. To examine the effects of adherence and MI elements, we will contrast Arms 2 vs. 3 across months 2, 4, and 6, comparing: (a) % cumulative light box purchase; (b) % cumulative compensation for light box purchase; and (c) mean EMA-adherence (aka, dose). We will conduct these analyses using methods similar to those for secondary outcomes; however, the analysis sample will be restricted to Arms 2 and 3. We will describe similar metrics in the TAU condition (Arm 1).

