The study treatment participants may utilize as a result of participating in this study may help improve their well-being and functioning and reduce mental health problems. Additionally, participants often feel good that participating in research may help other people.

10. Economic Burden to Subjects

There are no costs to participants for study assessments or study phone coaching activities. However, participants may incur the following costs during participation:

- Usual care underlies all three arms of the study, and some of that usual care may be directed at depression. Participants may incur costs for usual care; e.g., co-pays; paying for treatment, therapies, or other interventions. However, the delivery of these usual care services will be at the discretion of the KP providers, or community providers for usual care services participants may receive outside of KP.
- Participants in study arms 2 and 3 will be encouraged, but not required, to purchase a light box with an estimated cost of \$70 to \$200 depending on the model. All of these participants will be provided with written information about obtaining compensation (up to \$80 in Fred Meyer gift

cards) for this purchase through the study. In Arm 3, a study coach will guide participants to obtain compensation. Participants will be responsible for any purchase price greater than \$80. The study light box compensation process is modeled to simulate the KP durable medical equipment (DME) benefit, which does not currently cover LBs for non-SAD depression. Preliminary conversations with the DME decision group seem to indicate willingness to cover LBs for non-SAD depression when a published meta-analysis determines that there is sufficient evidence of LB benefit for non-SAD depression. While there are individual studies showing LB benefit for non-SAD depression, this evidence does not quite meet the threshold for changing the DME benefit.

Participants will be informed of these potential costs in the consent information form and during the recruitment call with our staff.

11. Compensation to Participants

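### The SAP's second process outcome counts reimbursement from the insurer's equipment benefit, whereas the protocol's counts gift-card compensation that the study itself pays; the SAP should be aligned

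*SAP*

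**What the plan says.** The SAP (BLT process outcomes) contrasts Arms 2 and 3 at months 2, 4 and 6 on three items: light box purchase, "cumulative DME reimbursement", and mean adherence from the EMA surveys. The stated purpose is to confirm that the Arm 3 elements did what they were meant to do. SAP Aim 1.1 has the Arm 3 coaches "assist with obtaining insurance reimbursement".

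The protocol (section 6, Data Analysis, BLT process outcomes) has the same three-item list, but its second item is "cumulative compensation for light box purchase". The paragraph on compensation for BLT purchase, also in section 6, says that the study pays up to $80 in gift cards, that Arm 3 coaches help participants obtain it, and that Arm 2 gets the same written information without a coach. The arrangement imitates "the KP durable medical equipment (DME) benefit, which does not currently cover LBs". Protocol section 10 describes the same scheme for Arms 2 and 3 but words the coverage gap more narrowly: a benefit "which does not currently cover LBs for non-SAD depression".

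Protocol section 5b admits patients with a new SAD diagnosis. Protocol section 2 lists the compensation program for light box purchase among the things whose feasibility the pilot will estimate.

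**The concern.** The two documents name different events with different payers. Coaches in this trial help participants obtain study gift cards; the SAP counts payments from an insurance benefit that the protocol says is not available for these devices, or not for most of this population. An analyst who follows the SAP would count an event that the intervention does not aim at, and would miss the one it does.

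Two things are at stake. One of the three contrasts meant to show that the Arm 3 elements worked would carry little or no information. And the protocol's compensation-program objective would be left without an analysis: the feasibility sentence in SAP Aim 2 covers recruitment, retention and adherence but not compensation, and no other SAP outcome measures it. Item (a) already captures purchase. What item (b) adds is whether buyers succeed in getting paid, which is where coach help differs from written guidance.

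**Working it through.** Neither document gives an expected rate or power for this outcome, so there is no figure of the plan's to reproduce. The check sets the texts side by side and then asks how much a literal DME outcome could show.

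**Side by side**

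| Item | SAP | Protocol |
|---|---|---|
| Process outcome (b) | DME reimbursement | Compensation for light box purchase |
| What Arm 3 coaches help obtain | Insurance reimbursement | Study gift cards, up to $80 |
| DME coverage of light boxes | Not discussed | None (section 6); none for non-SAD depression (section 10) |
| Feasibility of the compensation program | Not listed in Aim 2 | Listed in section 2 |

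**Inputs from the documents.** SAP sample 90, allocated 1:1:1, so 90/3 = 30 per arm and 60 in the comparison. Two-sided alpha of 0.05 is stated for the PHQ-9 power calculation and assumed here.

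**Case 1: no light box is covered (protocol section 6).** The result is 0/30 versus 0/30. The logistic model that the SAP carries over from its secondary outcomes cannot estimate an arm effect, and Fisher's exact test has power 0.

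**Case 2: SAD participants are covered (one reading of section 10).** Expected DME rate = SAD share × purchase rate, assuming that purchase does not depend on SAD status and that every covered buyer claims. Neither the SAD share nor the purchase rates are in the documents; the values below are assumptions. Fisher power is the sum of the binomial probabilities of all pairs of counts with exact p ≤ 0.05.

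| Purchase, Arm 2 / Arm 3 | SAD share | DME rate, Arm 2 / Arm 3 | Expected events out of 30 | Fisher power |
|---|---|---|---|---|
| 20% / 50% | 5% | 1.0% / 2.5% | 0.3 / 0.75 | <0.001 |
| 20% / 50% | 20% | 4% / 10% | 1.2 / 3.0 | 0.02 |
| 20% / 50% | 30% | 6% / 15% | 1.8 / 4.5 | 0.07 |
| 30% / 60% | 5% | 1.5% / 3.0% | 0.45 / 0.9 | <0.001 |
| 30% / 60% | 20% | 6% / 12% | 1.8 / 3.6 | 0.03 |
| 30% / 60% | 30% | 9% / 18% | 2.7 / 5.4 | 0.08 |
| 20% / 70% | 5% | 1.0% / 3.5% | 0.3 / 1.05 | <0.001 |
| 20% / 70% | 20% | 4% / 14% | 1.2 / 4.2 | 0.09 |
| 20% / 70% | 30% | 6% / 21% | 1.8 / 6.3 | 0.23 |

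For example, 0.20 × 0.70 = 0.14, and 30 × 0.14 = 4.2. Even where some events occur, an empty Arm 2 is a real possibility: (1 − 0.01)^30 = 0.74 at a 1% rate and (1 − 0.06)^30 = 0.16 at 6%. An empty arm again leaves the logistic odds ratio without a finite estimate.

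**The protocol's outcome on the same assumptions.** If every purchaser receives study compensation, the rates are the purchase rates themselves. Fisher power is then 0.60 for 20% versus 50%, 0.56 for 30% versus 60%, and 0.97 for 20% versus 70%. These figures show only that the outcome is able to differ between arms; they do not predict the result.

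**The case against.** The strongest reply is that the SAP phrase is a leftover label. The protocol describes the gift cards as imitating the DME benefit, so the SAP's authors may mean the simulated benefit. The SAP also differs from the protocol on the number of coaching calls (2-4 against 2-6) and the sleep scale (ISI against PSQI). That explanation is plausible, and on that reading the outcome is not stuck at zero. It does not remove the need for the edit: the SAP nowhere mentions study compensation, and its Aim 1.1 speaks of insurance.

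Four stronger inferences are tempting and are not supported:

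- That the rate must be exactly 0% whatever the coaches do. Section 10 limits non-coverage to non-SAD depression, and SAD patients are eligible. Some DME payments are possible, though perhaps few, since the study scheme is offered to everyone in Arms 2 and 3.
- That the trial would report coaching as ineffective. With no events, the contrast cannot be estimated, which is not a null result, and the team would know that it had issued gift cards.
- That the analysts would extract insurance claims. The SAP names no data source, and the protocol's list of source records does not mention DME claims.
- That the main conclusions are at risk. The SAP (Rationale and research questions) names initiation of BLT and adherence as its primary process outcomes; purchase and EMA adherence address these and are untouched.

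**Conclusion.** The point holds as a mismatch of outcome between SAP and protocol, confined to one of three process outcomes. Taken literally, the SAP item is inestimable if no light box is covered. If SAD participants are covered, it is uninformative at assumed SAD shares of 5 to 20% (expected rates of about 1 to 6% against 2.5 to 14%, exact power at most 0.09) and still weak at 30% (at most 0.23). These figures rest on assumed SAD shares and purchase rates, 30 per arm with all randomized as the denominator, and every covered buyer claiming. The mismatch itself, and the absence of an SAP outcome for the compensation-program objective, rest on the texts alone. It should be corrected before analysis; it does not bear on the PHQ-9 results.

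**What to change.** 1. In the SAP, BLT process outcomes, replace item (b) with the cumulative percentage receiving study compensation for a light box purchase by months 2, 4 and 6. Use everyone randomized to the arm as the denominator: restricting to purchasers would condition on something that coaching is meant to change.
2. Name the study's own compensation records as the source. The protocol's list of source records does not include them, and the intervention contact form on that list is kept for Arm 3 only, so it cannot serve both arms.
3. In SAP Aim 1.1, change the insurance wording to study compensation, and add the compensation program to the feasibility sentence in Aim 2.
4. Reconcile protocol sections 6 and 10 on whether the DME benefit covers light boxes for SAD. If it does, state how a DME payment to a SAD participant is counted.

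The cost is a few phrases in the SAP, one clarification in the protocol and an entry in the SAP revision table. Design, sample size and participant procedures do not change.
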